4.2 Study Intervention Phase

Aim 1: No intervention

Aim 2: No intervention

Aim 3: The discussion of the intervention phase is strictly for Aim 3 of the study project.

For the Aim 3 RCT phase, the participants randomized to the standard of care group will not undergo the health coaching intervention. The participants randomized to the health coaching group will attend health coaching sessions at the baseline, 1-week, 1-month and 3-month visits.

4.2.1 Follow up Visit 1

Aim 1: N/A

Aim 2: N/A

Aim 3: Both the health coaching group and the standard of care group will complete follow-up surveys at the 6-month follow-up visit.

4.3 Unscheduled Visits

Aim 1: There will be no unscheduled visits for the virtual or in-person focus groups or in-depth interviews.

Aim 2: There will be no unscheduled visits for the provider interviews.

Aim 3: Research staff will attempt to be flexible with unscheduled visits and conduct a study visit if the participant is within the time frame for their next visit. If the participant is not within the time frame for their next visit, the study staff will reschedule the participant for another time.

4.4 Subject Completion/Withdrawal

Aims 1, 2, 3: Participant completion of the study will be closely monitored in both treatment arms. Our criteria for defining study completion, withdrawal, drop out, and attrition is defined below.

Multiple attempts will be made to retain participants in the study. Participants in either treatment group who do not attend a visit after 3 unsuccessful contact attempts will be considered a no-show for that visit.

Subjects may withdraw from the study at any time without prejudice to their care. They may also be discontinued from the study at the discretion of the Investigator for lack of adherence to visit schedules. The Investigator may also withdraw subjects who violate the study plan, or to protect the subject for reasons of safety or for administrative reasons. It will be documented whether or not each subject completes the study. If the Investigator becomes aware of any serious, related adverse events after the subject completes or withdraws from the study, they will be recorded on the CRF.

Participants will be asked to provide at least three forms of secure contact information (e.g., cell phone, email, social media). In addition, participants will be asked about preferred method of contact, and will be asked for consent to text message. At the end of each study visit, participants will be scheduled for their next visit. We will use flexible visit windows for each coaching visit. Before the window opens, participants will be contacted via their preferred method to confirm their next appointment. If a participant does not respond after 2-3 attempts using one strategy (i.e., texting, emailing, calling) then a new outreach strategy will be used to diversify the approach. If a participant does not respond after five unanswered attempts, we will stop trying. Study staff will provide reminder contact (text, call or email) prior to each visit based on the participants preferred method. To facilitate follow up, the coaching sessions will not be restricted to the clinic, and instead coaches will

be able to meet youth in the community or over a CHOP-approved HIPAA compliant platform.

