Aim 3: We will conduct 1) an iterative pilot phase followed by 2) a small RCT assessing intervention effect on the intermediate target of prevention self-efficacy. Pilot testing will occur over a 3-month period to prime intervention for implementation, with the aim of recruiting n=10 pilot participants. Pilot phase participants will follow the same study procedure timeline as participants randomized to the coaching intervention arm of the RCT, excluding the 6-month follow-up visit. Pilot participants will not be followed in the RCT or contribute outcome data. At the end of every health coaching visit (the baseline, 1-week, 1-month and 3-month visits), pilot phase participants will complete a brief feedback interview to ensure face validity and identify areas needing refinement. Feedback will be incorporated into the study design, with amendments submitted to the IRB as needed. The RCT will randomize youth with recent STI 1:1 to the coaching intervention vs a standard of care (SOC) control. If difficulty retaining coaching participants during the RCT generates a disparity in evaluable participants per arm, the RCT's randomization scheme will be changed to 2:1, intervention vs SOC, to balance numbers of evaluable participants per arm. Both arms (intervention and SOC) will have data collection visits at the baseline, the 3-month, and the 6-month-follow-up time points. In addition, the intervention group will have health coaching sessions at baseline, 1 week, 1 month and 3 months. At the end of the 3-month health coaching visit, a sample of RCT phase participants assigned to the intervention arm will complete a brief feedback interview to ensure face validity and identify areas needing refinement for future studies.

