3.1.3 Follow-up Phase

Aim 1: No intervention

Aim 2: No intervention

Aim 3: All RCT participants will have a 6-month follow-up visit. Participants in the intervention arm will be able to attend the follow-up visit if they attend at least one of the health coaching visits. For both arms, the follow up visit will consist of the same data collection (CASI and chart abstraction) as the 3-month visit.

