6.3.2 Analysis

Aim 1: We will conduct a deductive qualitative analysis of focus group transcripts and in-depth interview transcripts with our theoretical model guiding the coding process. Codes related to model constructs will be assigned to interview segments to organize the data, using the software NVivo, with two study team members separately reviewing the first 10 transcripts line by line, assigning codes as concepts become apparent. We will compare text segments to those that have been previously assigned the same code, and to segments coded separately by each analyst, to decide whether they reflect the same concept. We will use this process to generate a coding scheme, then apply it to all transcripts. Once coding is complete, we will review the data to document emerging themes-general insights gleaned from the entirety of the data- which may inform intervention content.

Aim 2: Survey data will be summarized via descriptive statistics. We will set a >80% threshold for high acceptability, feasibility and appropriateness. The interview coding process will parallel that described in Aim 1. We will use an integrated deductive and inductive coding approach. Transcripts will be reviewed using deductive methodology, where CFIR determinants will be used as the coding framework. After completion, the transcripts will be re-reviewed using inductive methodology where codes identifying novel barriers and facilitators of implementation that do not map onto the CFIR will be identified and used to develop a coding framework that is then applied to all transcripts. We will integrate the qualitative and quantitative data by merging findings through a comparative coding analysis. The AIM and FIM scores will be dichotomized (completely disagree/disagree vs completely agree/agree). We will compare the distribution of content themes between providers with high vs low acceptability and, separately, high vs low feasibility ratings. Data will then be used as a starting point in which to build an optimized PrEP-inclusive coaching implementation strategy to be tested in the subsequent RCT.

Aim 3: The primary analysis will be based on an intention to treat approach and will include all subjects randomized at Visit 1.

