9.1.2 Blinding

There will be no patient or study team blinding. Due to the nature of the intervention, there could not be blinding to which study arm the participants are in.

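### Section 4.4 permits discontinuation from the whole study for missed visits without protecting outcome follow-up, which could cause arm-dependent loss of the primary outcome in Aim 3

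*Combined protocol and SAP*

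**What the plan says.** All references are to the combined protocol and SAP.

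- **Discontinuation (4.4).** The section covers all three aims and refers to both treatment arms. It says of participants: "They may also be discontinued from the study at the discretion of the Investigator for lack of adherence to visit schedules". It sets no number of missed visits and does not say whether surveys and chart abstraction continue afterwards.
- **Ordinary consequence of a missed visit (4.4).** "Participants in either treatment group who do not attend a visit after 3 unsuccessful contact attempts will be considered a no-show for that visit".
- **Visits (3.1 and Table 1).** "Both arms (intervention and SOC) will have data collection visits at the baseline, the 3-month, and the 6-month-follow-up time points". Beyond that, "the intervention group will have health coaching sessions at baseline, 1 week, 1 month and 3 months".
- **Blinding (9.1.2).** "There will be no patient or study team blinding".
- **Month-6 access (3.1.3).** All RCT participants are said to have this visit, but also: "Participants in the intervention arm will be able to attend the follow-up visit if they attend at least one of the health coaching visits". No matching condition is set for SOC.
- **Month-6 surveys (4.2.1).** Both groups are to complete them.
- **Analysis set (6.3.2).** "The primary analysis will be based on an intention to treat approach and will include all subjects randomized at Visit 1". The primary model uses scores at baseline, 3 and 6 months. No missing-data method or sensitivity analysis is named.

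**The concern.** The primary outcome is the change in modified GSES score from baseline to six months, so the trial depends on obtaining the month-6 survey from as many randomised participants as possible, by the same process in both arms. Section 4.4 gives an unblinded investigator a power that can end a participant's whole study involvement because of attendance. The attendance demands differ by arm. Two of the coaching arm's visits (1 week and 1 month) are intervention sessions with no SOC counterpart, so missing them is non-adherence to the intervention and not a failure to give outcome data.

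If the power is used, and if poor attenders gain less self-efficacy than good attenders, the coaching participants who still have a month-6 score would be a favourable selection. The comparison would then lean towards an analysis of adherers, although the plan states intention to treat.

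**Working it through.** **The plan's own figures.** The plan gives no figure for discontinuation. The nearest are in 6.4: an allowance of 10% loss, not split by arm (0.10 × 75 = 7.5 per arm), and a detectable difference of 0.7-0.9 SD. For the latter, with 67.5 per arm after 10% loss and a change-score SD of √(2(1−ρ)):

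(z₀.₉₇₅ + z₀.₈₀) × SD × √(2/67.5) = 2.802 × 1.407 × 0.1721 = 0.68 at ρ = 0.01, and 2.802 × 1.183 × 0.1721 = 0.57 at ρ = 0.3.

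The stated range is therefore not reproduced. It is conservative against this calculation, and the mismatch has no bearing on the present point.

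**Visits before month 6 (3.1, Table 1).** Coaching: 1 week, 1 month, 3 months, so three. SOC: 3 months, so one.

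**Shift in a comparison of retained participants.** Let h and s be the fractions discontinued in the coaching and SOC arms, and let discontinued participants change g SD less than retained ones in the same arm. An arm's full mean equals its retained mean minus (fraction lost × g), so the contrast among retained participants is shifted by (h − s) × g.

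Assume h − s = 0.10 and g = 0.5 to 1.0. Neither value comes from the documents. Then:

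- 0.10 × 0.5 = 0.05 SD
- 0.10 × 1.0 = 0.10 SD

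Against the plan's 0.7-0.9 SD this is 0.05/0.9 = 6% to 0.10/0.7 = 14%.

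**Sensitivity to how often the power is used.** Assume the same probability p of discontinuation at each scheduled visit in both arms. Then s = p and h = 1 − (1 − p)³.

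| p (assumed) | SOC loss | Coaching loss | Overall loss | Shift, g = 0.5 | Shift, g = 1.0 |
|---|---|---|---|---|---|
| 2% | 2.0% | 5.9% | 3.9% | 0.02 | 0.04 |
| 5% | 5.0% | 14.3% | 9.6% | 0.05 | 0.09 |
| 10% | 10.0% | 27.1% | 18.5% | 0.09 | 0.17 |
| 15% | 15.0% | 38.6% | 26.8% | 0.12 | 0.24 |

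At p = 5% the overall loss lies within the 10% allowance while coaching loss is almost three times SOC loss. Meeting the allowance therefore gives no protection against imbalance. At that p the detectable change-score difference is 0.57-0.68 SD, the same to two decimals as with an even 10% loss, so the main issue is bias and not power.

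**What the planned model can do.** A mixed model keeps the baseline and any 3-month score of a discontinued participant, so the table does not give the bias of the planned analysis. The model corrects for missingness only as far as the data in it explain that missingness. Coaching attendance and the investigator's judgement are not in the primary model described in 6.3.2.

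**The case against.** The strongest reply is that the plan as a whole intends to keep poor attenders. Section 4.4 says participants may be discontinued, not that they will be. Its ordinary consequence for a missed visit is a no-show for that visit, in either arm. It promises repeated contact by several routes, flexible windows, and coaching off-site or remotely. Section 3.1.3 keeps month 6 open to anyone who attended one coaching session, 4.2.1 expects month-6 surveys from both groups, and 9.7 pays both arms for the six-month visit and offers a feedback survey to coaching participants who missed later sessions.

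Much of this stands, and three stronger readings that a reader might infer are not supported:

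- *That the rule does remove outcome data unevenly.* It is a permission. No rate or threshold is given, so the documents show a possibility and not an effect.
- *That it breaks the intention-to-treat set.* Discontinuation takes no one out of the set of all randomised. It may leave later scores missing. The only removal of collected data described (4.4.1) is at the participant's own request.
- *That it creates the imbalance behind a switch to 2:1 allocation.* Sections 3.1 and 3.2 attribute that imbalance to difficulty in retaining coaching participants, not to removal by the investigator.

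The reply does not dispose of the point. None of these passages limits the discretion in 4.4 or says that outcomes are still sought once it is used, and the survey offered in 9.7 to those who missed sessions is a feedback survey, not the GSES. Nor would amending the one-session condition in 3.1.3 be enough, because 4.4 also reaches participants who attended some sessions and missed others.

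**Conclusion.** The concern holds as a risk that the plan permits and does not control. Use of the discretion in 4.4 could produce arm-dependent missing 3- and 6-month GSES scores, leave some intention-to-treat participants without the primary outcome, and bias the comparison. The direction would favour coaching if those discontinued would have gained less, which is plausible but not shown in the documents. Section 4.4 also sits awkwardly with 3.1.3, 4.2.1 and 6.3.2.

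The size cannot be derived. The 0.05-0.10 SD figure rests on an assumed 10-point excess in coaching discontinuation and an assumed deficit of 0.5-1.0 SD, and it applies to a comparison of retained participants. A reader might also work out that, if each visit is missed independently with probability 10-20%, 27-49% of coaching participants miss at least one visit before month 6 against 10-20% of SOC participants (1 − 0.9³ = 0.271; 1 − 0.8³ = 0.488). Those are chances of missing a visit under an assumption. They are not discontinuation rates and should not be read as expected loss.

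The matter is worth settling during conduct, because scores that were never collected cannot be recovered at analysis.

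**What to change.** For Aim 3, amend 4.4 to state that:

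1. missed visits or non-attendance at coaching do not end outcome follow-up;
2. the 3- and 6-month CASI and chart abstraction are attempted in both arms unless the participant withdraws consent for follow-up;
3. the study record shows which component stopped (coaching, surveys or chart review) and why.

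Reconcile 4.4 with 3.1.3, 4.2.1 and 6.3.2 so that all four say the same about who is followed to month 6, and say in 6.3.2 how missing outcomes are handled.

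Leave the safety and administrative grounds for withdrawal as they are. Restricting investigator withdrawal to safety alone would go further than this point supports. The change sets no rule on when coaching itself stops.

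The cost is amendment wording and some extra contact attempts for poor attenders. The 3- and 6-month visits are already scheduled and paid for in both arms.

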4.4.1 Early Termination Study Visit

Aims 1, 2, 3: If a visit is interrupted due to external factors, attempts will be made to resume at the earliest possible time, and resultant data will be handled in the same fashion as survey collection and interviews completed in one sitting. Participants who withdraw from the survey or interview prior to completion will be offered the option of having their earlier responses redacted from the record. If they choose to do so, any data collected for that participant will be excluded from all analyses. If participants elect to end an interview early but allow use of data already collected or if interviews are truncated due to external factors and unable to be completed, responses will be collected and handled according to standard study procedures. Analysis of data from partial interviews will be included in the study for the questions or portions of the survey and/or interview which were completed.

5 STUDY EVALUATIONS AND MEASUREMENTS

5.1 Screening and Monitoring Evaluations and Measurements

5.1.1 Aim 1

5.1.1.1 Focus groups or In-depth interviews

Five audio recorded in-person, or video recorded virtual focus groups will be conducted ~50 participants, 5-8 per group.

Focus groups and in-depth interviews will identify HIV/STI prevention barriers and facilitators and preferences for an intervention format across different demographic populations of adolescents. We will conduct separate focus groups for the following populations: cisgender females, heterosexual males and YMSM/TW, and a mixed sex/sexual orientation group of adolescents with identified depression on their annual primary care screening. Participants will have the option to complete an in-depth interview if they wish to not participate in the focus group, as described in section 4.1. Identifying key content themes and delivery preferences among different demographic groups and youth with mental health conditions will allow for enhanced tailoring of content for different adolescent user groups. For example, if youth with depression are more likely to identify medication self-efficacy as a barrier to PrEP uptake, intervention content can be tailored for this population to emphasize PrEP adherence strategies.

Focus groups will occur in-person, or if necessary, via virtual video conferencing using a HIPAA compliant CHOP approved vendor. Focus groups will start with an informational session on HIV/STI prevention strategies (PrEP, condoms, HIV/STI testing, and partner notification). We will then facilitate the focus group to identify the most salient barriers/ facilitators for each prevention strategy within each focus group. In the second half of the focus groups, we will focus on adolescent preferences for the delivery of sexual health care, and delivery of the proposed intervention. Youth will then share their preferences. Focus groups will last 1-2 hours. The individual in-depth interviews will occur in-person, via

phone, or video conferencing using a HIPAA compliant CHOP approved vendor. These interviews will focus on youth preferences for sexual health care in primary care, using the participant's own prior sexual health encounters in primary care as the framework for the interview. Given the sensitive nature of the topic, youth have the option to opt out of any of the interview questions (see appendix). In-depth interviews will last 30-45 minutes.

5.1.1.2 Survey Questionnaire

Prior to focus group participation, participants will complete a brief survey in-person, or via an emailed REDCap link, which will take approximately 15 minutes and will be used to assess demographics and sexual health measures. This will include questions of hearing of, accessing, and plans to start PrEP. We will measure knowledge of prevention strategies like PrEP and targets, including demographics and sexual behavior via CASI in REDCap. For participants who consented in-person, they will have the option to complete the survey in-person at the time of informed consent. For those participants recruited via phone or email, they will complete the survey via a REDCap link emailed to them before the virtual or in-person focus group or interview.

5.1.1.3 Electronic Medical Record Review

As part of the study, the study team will review the CHOP medical record of the participants for particular variables:

- STI diagnoses (gonorrhea, chlamydia, syphilis, trichomonas)
- Mental health diagnoses: derived from the problem list in the general EPIC chart. No data will be accessed from protected mental health encounters.

This information will be taken through the CHOP EPIC system as well as our team's QlikView database. The QlikView data visualization platform contains STI diagnosis data that is derived from EPIC and relayed from the CHOP data warehouse. These data will be used to confirm STI and mental health diagnosis from screening.

5.1.2 Aim 2

5.1.2.1 Chart simulated recall

Prior to the CSR, providers will receive a brief educational session about health coaching and PrEP. The CSR will then provide data on clinician decision making around PrEP and comprehensive HIV prevention delivery. Chart-simulated recall is a well-validated method in which providers review charts of their own patient encounters to understand clinical decision making and rationale for clinical behavior. Study staff will randomly select 3-4 charts of visits where an STI diagnosis was made. Clinicians will be asked to give a 1-2 sentence summary of the encounter including the patient's age, sex, chief complaint, and mental health comorbidities. With the EHR available for reference, we will ask participants what factors facilitated or hindered delivery of HIV and STI prevention care, including PrEP counseling or initiation, HIV testing, discussion of partner notification. We will ask if and how mental health co-morbidities affected with delivery of prevention care. These data will be used to understand how and when clinicians may best refer to the coaching intervention.

5.1.2.2 *In-depth interview*

Additional interview questions will be grounded in the Consolidated Framework for Implementation Research (CFIR) which includes five core constructs associated with effective implementation: 1) characteristics of the intervention: acceptability of PrEP and coaching, and advantages to current care; 2) outer setting: perception of patient needs and impact of mental health comorbidities; 3) inner setting: characteristics of the primary care system and implementation climate for PrEP and coaching; 4) characteristics of individual provider: knowledge, beliefs, and self-efficacy for HIV/STI prevention care, including PrEP prescription; and 5) implementation process: attitudes toward integrating comprehensive HIV and STI prevention in primary care.

5.1.2.3 *Computer Assisted Survey Instruments*

Acceptability of the proposed coaching intervention in primary care will be measured via the Acceptability of the Intervention Measure (AIM). Feasibility, the extent to which the intervention could be successfully implemented within the setting, will be measured by the Feasibility of Intervention Measure (FIM). Appropriateness, the perceived fit of the intervention and relevance for the practice setting, will be measured with the Intervention Appropriateness Measure (IAM).

5.1.3 Aim 3

5.1.3.1 *Computer Assisted Survey Instruments (baseline, 3-month and 6-month visit)*

The CASI will take approximately 40 minutes. These data will be entered directly into the secure REDCap platform by participants, with the option of having the survey read aloud and entered by study staff if the participant prefers. We will measure theorized intervention predictors and targets including demographics, sexual behavior, health activation, stigma, and self-efficacy. Surveys are:

Background/Demographics
Current Prevention Practices
Intentions Questions
Self-Efficacy
Knowledge and Attitudes Survey
Confidence in Safer Sex Scale
CRAFFT
General Self Efficacy Scale (GSES)
HIV Knowledge and Attitude
Modified ACES Inventory
Modified Partner Communication
Parent Adolescent Communication
Sexual Self Efficacy Scale
Youth Pediatric Symptom Checklist

Interpersonal Reactivity Index (IRI)
 Inventory of Parent and Peer Attachment (IPPA)
 Coaching Satisfaction Survey

